11 SAFETY

11.1 Definition of Adverse Events

The term adverse event covers any unfavorable and unintended sign, symptom, syndrome, or illness that develops or worsens during the period of observation in the clinical study, reported for 100 days (3 months) post last treatment.

Clinically relevant abnormal results of diagnostic procedures including abnormal laboratory findings (e.g., requiring unscheduled diagnostic procedures or treatment measures, or resulting in withdrawal from the study) are considered to be adverse events.

Worsening of a sign or symptom of the condition under treatment will normally be measured by efficacy parameters. However, if the outcome fulfills the definition of “serious adverse event”, it must be recorded as such.

The adverse event may be:

- A new illness
- Worsening of a concomitant illness
- An effect of the study medication, including comparator
- A combination of two or more of these factors

No causal relationship with the study medication or with the clinical study itself is implied by the use of the term “adverse event”.

Adverse events fall into the categories “non serious” and “serious”.

Surgical procedures themselves are not adverse events; they are therapeutic measures for conditions that require surgery. The condition for which the surgery is required is an adverse event, if it occurs or is detected during the study period. Planned surgical measures permitted by the clinical study protocol and the condition(s) leading to these measures are not adverse events, if the condition(s) was (were) known before the start of study treatment. In the latter case the condition should be reported as medical history.

The following laboratory abnormalities should be documented and reported appropriately:

- Any laboratory test result that is clinically significant or meets the definition of an SAE
- Any laboratory abnormality that required the participant to have study drug discontinued or interrupted
- any laboratory abnormality that required the subject to receive specific corrective therapy.

It is expected that wherever possible, the clinical rather than laboratory term would be used by the reporting investigator (eg, anemia versus low hemoglobin value).

11.2 Serious Adverse Events

- Death.
- Life-threatening.¹
- Unplanned hospitalization or prolongation of existing hospitalization (for > 24 hours).²
- Persistent or significant disability or incapacity.³
- Pregnancy
- Congenital anomaly or birth defect.
- Is an important medical event.⁴
- Drug-induced liver injury (DILI).⁵

¹ “Life-threatening” means that the subject was at immediate risk of death at the time of the serious adverse event; it does not refer to a serious adverse event that hypothetically might have caused death if it were more severe.

² The following hospitalizations are not considered SAEs:

- Hospitalization < 24h
- Planned hospitalization required by the protocol (e.g., for study drug administration or to perform an efficacy measurement for the study)
- Hospitalization for a preexisting condition, provided that all of the following criteria are met:
 - The hospitalization was planned prior to the study or was scheduled during the study when elective surgery became necessary because of the expected normal progression of the disease.
 - The patient has not experienced an adverse event.
- Routine health assessment requiring admission for baseline/trending of health status (eg, routine colonoscopy)
- Admission encountered for another life circumstance that carries no bearing on health status and requires no medical/surgical intervention (eg, lack of housing, economic inadequacy, caregiver respite, family circumstances, administrative reason).

³ “Persistent or significant disability or incapacity” means that there is a substantial disruption of a person’s ability to carry out normal life functions.

⁴ Medical and scientific judgment should be exercised in deciding whether expedited reporting is appropriate in situations where none of the outcomes listed above occurred.

Important medical events that may not be immediately life-threatening or result in death or hospitalization but may jeopardize the patient or may require intervention to prevent one of the other outcomes listed in the definition above should also usually be considered serious. Examples of such events include allergic bronchospasm requiring intensive treatment in an emergency room or at home, blood dyscrasias or convulsions that do not result in inpatient hospitalization, or the development of drug dependency or drug abuse, or suspected transmission of an infectious agent (eg pathogenic or nonpathogenic) via the study drug, or overdose of treatment, or lab test abnormalities clinically significant.

A diagnosis of cancer during the course of a treatment should be considered as medically important. The List of Critical Terms (1998 adaptation of World Health Organization Adverse Reaction Terminology Critical Terms List, provided in the “Instructions for completing the ‘Serious Adverse Event/Expedited Report from a Clinical Trial’ form”) should be used as guidance for adverse events that may be considered serious because they are medically important.

⁵ Wherever possible, timely confirmation of initial liver-related laboratory abnormalities should occur prior to the reporting of a potential DILI event. All occurrences of potential DILIs, meeting the defined criteria, must be reported as SAEs. Potential DILI is defined as:

1) ALT or AST elevation >3 times upper limit of normal (ULN)

AND

2) Total bilirubin >2 times ULN, without initial findings of cholestasis (elevated serum alkaline phosphatase)

AND

3) No other immediately apparent possible causes of AST/ALT elevation and hyperbilirubinemia, including, but not limited to, viral hepatitis, pre-existing chronic or acute liver disease, or the administration of other drug(s) known to be hepatotoxic.

A hepatic AE management algorithm has been established according to nivolumab IB for appropriate management of DILI cases (cf; appendix II).

The following hospitalizations are not considered SAEs:

- A visit to the emergency room or other hospital department < 24 hours, that does not result in admission (unless considered an important medical or life-threatening event)
- Elective surgery, planned prior to signing consent
- Admissions as per protocol for a planned medical/surgical procedure
- Routine health assessment requiring admission for baseline/trending of health status (eg, routine colonoscopy)
- Medical/surgical admission other than to remedy ill health and planned prior to entry into the study. Appropriate documentation is required in these cases.
- Admission encountered for another life circumstance that carries no bearing on health status and requires no medical/surgical intervention (eg, lack of housing, economic inadequacy, caregiver respite, family circumstances, administrative reason).
- Admission for administration of anticancer therapy in the absence of any other SAEs (applies to oncology protocols)

Clarification of the difference in meaning between “severe” and “serious”

The term “severe” is often used to describe the intensity (severity) of a specific event (as in mild, moderate, or severe myocardial infarction); the event itself, however, may be of relatively minor medical significance (such as severe headache). This is not the same as “serious”, which is based on the outcome or action criteria usually associated with events that pose a threat to life or functioning. Seriousness (not severity) serves as a guide for defining regulatory reporting obligations.

SAEs/AEs will be reported up to 100 days (3 months) for both study drugs, and SAEs notification will be made within 24 hours.

11.3 Period of Observation

For the purposes of this study, the period of observation for collection of adverse events extends from the date of signature of the informed consent until 100 days after the last day of study treatment except for adverse events related to study drug, which must be reported during follow-up period until resolution or initiation of further anti-tumor therapy.

If an Investigator detects a serious adverse event in a study subject after the end of the period of observation, and considers the event possibly related to prior study treatment,

he or she should contact the Sponsor to determine how the adverse event should be documented and reported.

At each visit/assessment AEs will be assessed from information collected from the source documents and information transcribed into the CRF.

11.4 Documentation and Reporting of Adverse Events by Investigator

All adverse events that occur during the observation period set in this protocol must be documented on the pages provided in the case report form in accordance with the instructions for the completion of adverse event reports in clinical studies. These instructions are provided in the case report form itself.

The following approach will be taken for documentation:

- All adverse events (whether serious or non-serious, or considered as an alert term) must be documented on the “Adverse Event” page of the case report form.
- If the adverse event is serious, the investigator must complete, in addition to the “Adverse Event” page in the case report form, a “Serious Adverse Event/Expedited Report from a Clinical Trial” form at the time the serious adverse event is detected.

This form will be filled in the eCRF. In case of unavailability of the eCRF, a paper form will be sent by email to [contact].

Every attempt should be made to describe the adverse event in terms of a diagnosis. If a clear diagnosis has been made, individual signs and symptoms will not be recorded unless they represent atypical or extreme manifestations of the diagnosis, in which case they should be reported as separate events. If a clear diagnosis cannot be established, each sign and symptom must be recorded individually.

All patients who have adverse events, whether considered associated with the use of the investigational products or not, must be monitored to determine the outcome. The clinical course of the adverse event will be followed up according to accepted standards of medical practice, even after the end of the period of observation, until a satisfactory explanation is found or the investigator considers it medically justifiable to terminate follow-up. All questions on the completion and supply of adverse event report forms and any further forms issued to the investigator at a later date to clarify unresolved issues should be addressed to the IFCT.

11.5 Immediate Reporting by Investigators to IFCT

Serious adverse events and adverse events that fulfill a reason for expedited reporting to Pharmacovigilance must be documented on a “Serious Adverse Event/Expedited Report from a Clinical Trial” form in accordance with the “Instructions for completing the ‘Serious Adverse Event/Expedited Report from a Clinical Trial’ form”. This form must be completed and supplied to the Sponsor within 24 hours or at the latest on the following working day. The “Serious Adverse Event/Expedited Report from a Clinical Trial” form and the instructions are provided in the investigator’s study file.

The initial report must be as complete as possible, including details of the current illness and (serious) adverse event, and an assessment of the causal relationship between the event and the investigational product(s).

Information not available at the time of the initial report (e.g., an end date for the adverse event or laboratory values received after the report) must be documented on a follow-up “Serious Adverse Event/Expedited Report from a Clinical Trial” form.

The “Instructions for completing the ‘Serious Adverse Event/Expedited Report from a Clinical Trial’ form” give more detailed guidance on the reporting of serious adverse events, adverse events that comply with alert terms, and adverse events initially reported as non-serious that become serious. In the latter situation, when a non-serious event becomes serious, details must be forwarded immediately to the Sponsor on a “Serious Adverse Event/Expedited Report from a Clinical Trial” form.

11.6 Pregnancy/Exposure Reporting

If, following initiation of the investigational product, it is subsequently discovered that a study participant is pregnant or may have been pregnant at the time of investigational product exposure. This means pregnancies occurring in female participants, female partners of male participants, or females exposed through direct contact with the agent during their pregnancy (for example, environmental exposure involving direct contact with the agent). Pregnancies occurring up to 6 months after the completion of nivolumab must also be reported. The investigational product will be permanently discontinued.

The investigator is required to inform IFCT within 24 hours of learning of the pregnancy using the pregnancy reporting form. Follow-up information regarding the course of the pregnancy, including perinatal and neonatal outcome and, where applicable, offspring information must be reported on the Pregnancy reporting Form.

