4 ELIGIBILITY

4.1 Inclusion Criteria

1. Age ≥ 18 years old
2. HIV1 or HIV2, regardless of CD4 cell count
3. HIV Viral load <200 copies/mL
4. Proven histologically and/or cytologically, stage IIIB-IV or metastatic relapse post-surgery non-small cell lung cancer (NSCLC)
5. Disease recurrence or progression during/after at least one prior platinum doublet-based chemotherapy regimen for advanced or metastatic disease
6. Measurable disease by Computed tomography (CT)/Magnetic resonance imaging (MRI) per RECIST 1.1 criteria
7. Performance status (PS) 0, 1 or 2
8. Written informed consent
9. Patients must have adequate organ function: creatinine clearance > 40 mL/min (Cockcroft, MDRD or CKD-Epi formula or 24h Urine Calculate creatinine clearance from a 24h urine collection), neutrophiles count > 1500/mm³; platelets > 100 000/mm³ ; hemoglobine > 9 g/dL; hepatic enzymes < 3N with total bilirubin ≤ 1.5 × ULN (upper limit of normal) except subjects with documented Gilbert's syndrome (≤ 5 × ULN) or liver metastasis, who must have a baseline total bilirubin ≤ 3.0 mg/dL
10. Patients must receive appropriate care and treatment for HIV infection including ART when clinically indicated and subjects should be under the care of a physician experienced in HIV management. In case of recent introduction of cART and CD4 levels <50 cells/ml, inclusion will be possible provided subjects had at least 4 weeks of

treatment prior to inclusion, to avoid clinical type IRIS (immune inflammatory syndrome reconstitution). All antiretroviral treatments are allowed.

11. Females of childbearing potential who are sexually active with a nonsterilized male partner must use a highly effective method of contraception for 28 days prior to the first dose of investigational product, and must agree to continue using such precautions for 6 months after the final dose of investigational product; cessation of contraception after this point should be discussed with the referent physician. Periodic abstinence, the rhythm method, and the withdrawal method are not acceptable methods of contraception. They must also refrain from egg cell donation for 6 months after the final dose of investigational product. Men receiving nivolumab and who are sexually active with women of childbearing potential will be instructed to adhere to contraception (appendix I) for a period of 31 weeks after the last dose of nivolumab.

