15.6 Study schedule

The protocol should begin in June 2017. The trial recruitment period is expected to be 42 months. The study will be ended one year after the last treatment of the last patient. The trial should be ended by December 2021.

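### Pregnancy reporting stops at 6 months after nivolumab, although men must use contraception for 31 weeks, so about the last 5 weeks of the men's period carry no duty to report a partner's pregnancy

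*Protocol*

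**What the plan says.** Criterion 11 in Protocol section 4.1 sets contraception after treatment separately by sex. Women of childbearing potential "must agree to continue using such precautions for 6 months after the final dose of investigational product". Men whose partners could become pregnant are to adhere to "contraception (appendix I) for a period of 31 weeks after the last dose of nivolumab".

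Protocol section 11.6 then defines which pregnancies count for exposure reporting. Partners are named explicitly: "This means pregnancies occurring in female participants, female partners of male participants, or females exposed through direct contact with the agent during their pregnancy". For the time after treatment it gives one limit, with no distinction by sex: "Pregnancies occurring up to 6 months after the completion of nivolumab must also be reported". The same section asks for notification within 24 hours of the investigator learning of a pregnancy, and for follow-up to perinatal and neonatal outcome.

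Two other provisions could bear on a late pregnancy. Section 11.2 lists pregnancy among serious adverse events, but section 11.3 collects adverse events "until 100 days after the last day of study treatment except for adverse events related to study drug". Section 11.3 also has a route for later events, which begins: "If an Investigator detects a serious adverse event in a study subject after the end of the period of observation". It applies when the investigator considers the event possibly related to prior treatment.

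**The concern.** The protocol gives men a longer contraception period than women, and it puts their partners within the scope of pregnancy reporting. The reporting limit nevertheless follows the women's period only. A partner pregnancy that begins after 6 months but before 31 weeks arises while the man is still required to use contraception, yet nothing in the text requires it to be reported or followed to neonatal outcome. That is the kind of exposure such reporting exists to capture. The stake is completeness of safety information. The primary endpoint, the decision rule and participants' dosing are not touched.

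**Working it through.** The protocol states no figure for this gap, so there is none to reproduce. The check is calendar arithmetic on its two periods, followed by a search for any other provision that might cover the difference.

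**Inputs**
- Men's contraception period: 31 weeks after the last dose (section 4.1, criterion 11).
- Women's contraception period: 6 months after the final dose (same criterion).
- Pregnancy reporting limit: 6 months after completion of nivolumab (section 11.6).
- General adverse event window: 100 days after the last treatment (section 11.3).
- End of study: one year after the last patient's last treatment (section 15.6).

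The contraception periods and the reporting limit all run from the end of nivolumab dosing, so they can be compared directly.

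**Gap for partners of men**
- Men's period: 31 × 7 = 217 days.
- Six calendar months: 181 to 184 days depending on the start date; on average 6 × 365.25/12 = 182.6 days, or 26.1 weeks.

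| Length of 6 months | Gap in days | Gap in weeks | Share of 217 days |
|---|---|---|---|
| 184 days | 217 − 184 = 33 | 33/7 = 4.7 | 33/217 = 15.2% |
| 182.6 days (average) | 217 − 182.6 = 34.4 | 34.4/7 = 4.9 | 34.4/217 = 15.8% |
| 181 days | 217 − 181 = 36 | 36/7 = 5.1 | 36/217 = 16.6% |

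**Gap for female participants**

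6 months − 6 months = 0.

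**Does another provision cover days 185 to 217?**
- The 100-day window ends before either contraception period, so listing pregnancy as a serious adverse event in section 11.2 does not help.
- The exception in section 11.3 for drug-related adverse events does not name partner pregnancies.
- The late-event route in section 11.3 concerns a study subject, which a partner is not, and it also depends on a judgement of relatedness.
- The 24-hour rule in section 11.6 says how fast to notify. Reading it as a duty without end would leave the 6-month sentence with no function.

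**Would a 31-week limit outlast the study?**

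217/30.44 = 7.1 months, which is less than the 12 months between the last patient's last treatment and the end of the study.

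**The case against.** The best counter-argument is textual. The 6-month sentence is worded as an addition, and the paragraph on 24-hour notification and outcome follow-up has no end date. On that reading, a later partner pregnancy that comes to the investigator's notice would still have to be reported. The reading is possible but weak, because a duty with no end would make the 6-month sentence redundant, and most sites will take 6 months as the limit.

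It is also fair to say that the two provisions do not contradict each other. One governs contraception and the other reporting, and a site can comply with both. The protocol gives no reason for 31 weeks and nowhere says that reporting must last as long as contraception. That the men's period marks a time of possible exposure risk is inferred from the requirement itself. The inference is reasonable, especially as the two periods coincide exactly for women, but it remains an inference.

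Appendix I, which criterion 11 cites for men's contraception, is not in the text available here, nor is the pregnancy reporting form. Either could in principle contain a longer instruction. The appendix is cited for contraception, not for reporting, so this is a caveat and not an answer.

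Finally, the practical weight is very small. The trial has 30 patients, only partners of male participants matter, and the interval is about 34 days. Section 3 places the last study visit 4 weeks (± 1 week) after the last injection, so capture depends on the investigator learning of the pregnancy whichever limit is set. All of that stands, and it is why the point is minor.

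**Conclusion.** The point holds, as a minor one. The section 11.6 limit matches the women's contraception period and falls 33 to 36 days (about 5 weeks, 15% to 17%) short of the men's, although partners of men are expressly in scope. No other provision in the available text fills the interval.

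This rests on three assumptions: that the 6-month sentence is a limit on post-treatment reporting, that the men's contraception period is a sensible measure of how long partner pregnancies are of interest, and that Appendix I and the reporting form do not already set a longer period. The result has no bearing on the sample size, the efficacy analyses or the dosing of participants.

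**What to change.** Replace the single limit in section 11.6 with two: report pregnancies in female participants up to 6 months after the last dose, and pregnancies in the female partners of male participants up to 31 weeks after the last dose. The partner gap then becomes zero and the women's rule is unchanged. Check at the same time that Appendix I and the pregnancy form agree.

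The cost is one sentence. No visit is added and the study is not lengthened, since section 15.6 already provides that "The study will be ended one year after the last treatment of the last patient". At most there would be a rare extra pregnancy form.

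Two optional clarifications could go in with the same amendment, although the point does not depend on them: have the 100-day sentence in section 11.2 refer to section 11.6 for pregnancy, and state that the discontinuation sentence in section 11.6 applies to a participant who is herself pregnant.

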12 DOSE TOXICITIES AND ADJUSTEMENT

12.1 Dose reductions

There is no dose reduction for nivolumab.

12.2 Dose Delay

Nivolumab administration should be delayed for the following:

- Grade 2 pneumonitis
- Grade 2 or 3 diarrhea or colitis
- Grade 2 elevation in AST, ALT or total bilirubin
- Grade 2 or 3 creatinine elevation
- Symptomatic endocrinopathies (including hypothyroidism, hyperthyroidism, hypophysitis, adrenal insufficiency and diabetes)
- Grade 3 rash
- Any AE, laboratory abnormality or intercurrent illness which in the judgment of the investigator, warrants delaying the dose of study medication.

Subjects who require delay of nivolumab should be re-evaluated weekly or more frequently if clinically indicated and resume nivolumab dosing when re-treatment criteria are met.

